**Nature Made Nutritional Products**  
[name], U.S.A.  
[name] • [www.NatureMade.com](http://www.NatureMade.com)

USP has tested and verified ingredients, potency and manufacturing process. USP sets official standards for dietary supplements. [www.uspverified.org](http://www.uspverified.org)

†This statement has not been evaluated by the Food and Drug Administration. This product is not intended to diagnose, treat, cure or prevent any disease.

**VI. Research-related visits.** Data will be collected at baseline (<20 weeks gestation), 24-28 and 34-36 weeks gestation and at delivery. Tolerability [potential adverse events (AEs) (e.g., GI symptoms)] will be assessed via phone/email/text weekly for the first 4 weeks and bi-weekly thereafter. Compliance data will be collected at pill pick-up visits (scheduled around usual care prenatal visits whenever possible) and during research visits. Women will be called or texted and emailed 2-3 days prior to each research-related visit and reminded of their appointment time, location and instructions how to prepare (e.g., fast for 2 hours, bring their pill containers). The visits will take place at the Clinical Research Center [name]. The research-related visits and data collected at each visit are described below:

**a. Baseline (<20 weeks gestation).**

Reminder Phone Call or Text and Email: Women will be called or texted and emailed 2-3 days before the baseline visit. Women will be reminded of their appointment time and location, asked to not eat for at least 2 hours before the appointment, and reminded about the visit procedures.

Obtaining Informed Consent: Consent will be obtained using IRB approved materials by trained research staff at the baseline study visit before any study procedures take place.

Data collection procedures: Women will be weighed with an electronic scale; height measured (baseline only); a venous blood sample (30 ml) obtained by research staff; and surveys (described in detail below) will be interviewer administered by trained staff. Women will be asked to download the Pillsy app to their smart phones and instructions on how to use the Pillsy bottle and Pillsy app will be

given. If there is extra blood available from the venous blood sample and the patient consents, it may be used for future research to learn more about how to prevent, detect, or treat other health problems in pregnancy.

Surveys: Women will be asked to complete the following surveys at baseline:

1. Maternal Health History Questionnaire. This questionnaire was developed by the research team, and asks about maternal health history, maternal obstetric history, current and past medications, personal history, and demographics.
2. Food Frequency Questionnaire (FFQ). This questionnaire is a 125-item dietary assessment tool used to determine habitual food consumption over the past year.
3. 24-hour diet recall. The 24-hour diet recall will be collected using Nutrition Data System for Research (NDSR) software, a computer-based software application developed at the University of Minnesota that facilitates the collection of dietary recalls in a standardized fashion. Dietary intake data gathered by interview is governed by a multiple-pass interview approach. Dietary supplement use will be assessed in conjunction with collection of 24-hour dietary recalls using the Dietary Supplement Assessment Module included in NDSR. Use of all types of dietary supplements and non-prescription antacids are queried in the module. The RAs are NDSR certified through the University of Illinois Cancer Center Diet and Behavior Shared Resource.
4. GI symptoms checklist. This short survey probes for recent GI problems including abdominal pain, nausea, constipation, and diarrhea.
5. Mood and Anxiety Symptom Questionnaire – Anhedonia subscale (MASQ-AD). This is a 22-item subscale of the MASQ, a measure of depressive disorders.
6. Patient Health Questionnaire (PHQ-9). This is a 9-item questionnaire assessing depressive symptoms.
7. Edinburgh Postnatal Depression Scale (EPDS). This is a 10-item scale intended to measure depressive symptoms during the perinatal period.
8. Childhood Trauma Questionnaire (CTQ). This is a 28-item psychological screening for traumatic experiences during childhood.
9. Perceived stress scale. This is a 10-item scale intended to measure perceived stress over the last month.
10. Post-traumatic stress symptoms National Stressful Events Survey PTSD Short Scale (NSESSS). The National Stressful Events Survey PTSD Short Scale (NSESSS) is a 9-item measure that assesses the severity of posttraumatic stress disorder in individuals age 18 and older following an extremely stressful event or experience.
11. Adult violence exposure. This is a 29-item survey used to identify exposure to violence of the past 7 days. The survey is used to classify low- and high-violence exposure that has demonstrated good construct validity, internal consistency, test-retest reliability, and validity.
12. Major experiences of Discrimination. This is a 6-item measure to assess experience of major discrimination over the past year.
13. Social support – MOS social support survey. This survey was designed to be comprehensive in terms of recent thinking about the various dimensions of social support.

14. Spiritual Experience Index-Revised. A 23-item scale that measures faith and spiritual journey, aiming to not impose any particular faith as part of the questions.
15. Residential History. Residential history over the previous 10 years.
16. Healthy Pregnancy Stress Scale. This is an 18-item scale that measures pregnancy stressors women have experienced during their pregnancy.
17. Adverse Childhood Experiences. This is a 10-item scale that measures adverse childhood experiences.
18. Hair collection survey. This survey was developed by the research team and asks about hair care practices.
19. Short Scale Anxiety Sensitivity Index (SSASI). This is 5-item scale that measures anxiety.
20. Behavioral Inhibition System & Behavioral Activation System Scales. This is a 24-item scale that measures behavioral inhibition and activation.
21. Brief Irritability Test (BITe). This is a 5-item scale that measures irritability.
22. Generalized Anxiety Disorder 7-item (GAD-7) Scale. This is a 7-item scale that measures anxiety.
23. IDAS-II III Temper (Anger) Scale. This is a 5-item scale that measures anger.
24. Intolerance of Uncertainty Scale – Short Form. This is a 12-item scale that measures intolerance of uncertainty.
25. Pittsburgh Sleep Quality Index. This is a 24-item scale that measures sleep.

Hair collection: If the woman agrees, a sample of hair (70-100 strands) will be collected from the crown of her head (about 70-100 strands) by trained research staff.

Rectal Swab: If the woman agrees, using the kit provided, she will collect two rectal swabs.

***b. Research follow-up visits (24–28 and 34–36 weeks gestation)***

Reminder Phone Call, Text, and Email: Women will be called or texted and emailed 2-3 days before the visit. Women will be reminded of their appointment time and location, asked to not eat for at least 2 hours before the appointment, and reminded about the visit procedures.

Data collection procedures: Women will be weighed with an electronic scale; a venous blood sample (30 ml) obtained by research staff; 2 rectal swab samples collected, optional; and surveys (described in detail below) will be interviewer administered by trained staff. If there is extra blood available from the venous blood sample and the patient consents, it may be used for future research to learn more about how to prevent, detect, or treat other health problems in pregnancy.

Surveys: Women will be asked to complete the following surveys:

1. 24 hour diet recall. The 24-hour diet recall will be collected using Nutrition Data System for Research (NDSR) software, a computer-based software application developed at the University of Minnesota that facilitates the collection of dietary recalls in a standardized fashion. Dietary intake data gathered by interview is governed by a multiple-pass interview approach. Dietary supplement use will be assessed in conjunction with collection of 24-hour dietary recalls using

the Dietary Supplement Assessment Module included in NDSR. Use of all types of dietary supplements and non-prescription antacids are queried in the module. The RAs are NDSR certified through the University of Illinois Cancer Center Diet and Behavior Shared Resource.

2. GI symptoms checklist. This short survey probes for recent GI problems including abdominal pain, nausea, constipation, and diarrhea.
3. Mood and Anxiety Symptom Questionnaire – Anhedonia subscale (MASQ-AD). This is a 22-item subscale of the MASQ, is a measure of depressive disorders.
4. Patient Health Questionnaire (PHQ-9). This is a 9-item questionnaire assessing depressive symptoms.
5. Edinburgh Postnatal Depression Scale (EPDS). This is a 10-item scale intended to measure depressive symptoms during the perinatal period.
6. Perceived stress scale. This is a 10-item scale intended to measure perceived stress over the last month.
7. Adult violence exposure. This is a 29-item survey used to identify exposure to violence of the past 7 days. The survey is used to classify low- and high-violence exposure that has demonstrated good construct validity, internal consistency, test-retest reliability, and validity.
8. Social support – MOS social support survey. This survey was designed to be comprehensive in terms of recent thinking about the various dimensions of social support.
9. Healthy Pregnancy Stress Scale. This is an 18-item scale that measures pregnancy stressors women have experienced during their pregnancy.
10. Hair collection survey. This survey was developed by the research team and asks about hair care practices.
11. Short Scale Anxiety Sensitivity Index (SSASI). This is 5-item scale that measures anxiety.
12. Behavioral Inhibition System & Behavioral Activation System Scales. This is a 24-item scale that measures behavioral inhibition and activation.
13. Brief Irritability Test (BITe). This is a 5-item scale that measures irritability.
14. Generalized Anxiety Disorder 7-item (GAD-7) Scale. This is a 7-item scale that measures anxiety.
15. IDAS-II III Temper (Anger) Scale. This is a 5-item scale that measures anger.
16. Intolerance of Uncertainty Scale – Short Form. This is a 12-item scale that measures intolerance of uncertainty.
17. Pittsburgh Sleep Quality Index. This is a 24-item scale that measures sleep.

Hair collection (34-36 weeks only): If the woman agrees, a sample of hair will be collected from the crown of her head (70-100 strands) by trained research staff.

Rectal Swab (baseline, 24-28 and 34-36 weeks): If the woman agrees, using the kit provided, she will collect two rectal swabs.

Maternal health data: We will abstract from the EHR data pertaining to recent illness or infection, new medications, and change in health status (i.e., development of a pregnancy related condition like gestational diabetes).

Pill pick up and adherence monitoring (24-28 weeks and 34-36 weeks gestation):

We will monitor adherence using electronic pill monitoring technology Pillsy and standard pill counts. Women will get a new 30-40-day allotment of pills. During these visits, we will download data from the Pillsy app on their smart phones and conduct a physical pill count. If a woman is found to be non-compliant (i.e., consuming <75% of pills) with her permission, she will receive automated daily text messages around dinner time to help increase compliance with the supplement interventions.

**Pill pick up and adherence monitoring visits (approximately @ 18-19 weeks, 22-23 weeks, 30-31 weeks, 38-39 weeks).** We will monitor adherence using electronic pill monitoring technology Pillsy and standard pill counts. Women will visit UIC approximately every 28 days to get a new 30-40-day allotment of pills and for compliance to be assessed. If possible, these encounters will be coordinated around standard clinical prenatal care appointments. If not, separate pill pick up visits and under certain conditions home pill drop-off will be coordinated. During these visits, we will download data from the Pillsy app on their smart phones and conduct a physical pill count. If a woman is found to be non-compliant (i.e., consuming < 75% of pills) with her permission, she will receive automated daily text messages around dinner time to help increase compliance with the supplement interventions. We will administer the GI symptoms checklist at each visit.

- c. Feasibility and Tolerability. Feasibility will be based on accrual and withdrawal/loss to follow-up rates at the end of the study and adherence determined using the Pillsy smart bottles and standard pill counts. The intervention will be considered feasible if 50% of women approached for participation enroll, overall withdrawal rate is  $\leq 15\%$  and adherence to the supplement regimen is  $\geq 85\%$ . Tolerability [(potential adverse events (AEs) (e.g., GI symptoms)] will be assessed via phone/email/text using the Pillsy app weekly for the first 4 weeks and bi-weekly thereafter. The intervention will be deemed tolerable if no serious AEs (highly unlikely) are documented, and the rate of non-serious AEs is similar between study arms.

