## 2. Methods.

- I. **Research participants.** We will recruit and enroll 40 women early in pregnancy (< 20 weeks gestation) from the University of Illinois at Chicago (UIC) Obstetrics (OB) clinics located at the University of Illinois Hospital and Health Sciences System (UIHHSS) Outpatient Care Center, Center for Women’s Health. Women will be between the ages of 18 – 45 years old and at risk for maternal ID based on hemoglobin of 10.0 – 11.9 g/dl assessed as part of standard clinical care during the first prenatal OB visit.
- II. **Eligibility, recruitment, and informed consent:** After obtaining a waiver of consent for recruitment purposes, we will complete a pre-screen eligibility checklist of women < 20 weeks gestation who are seeking prenatal care at the UIC Obstetrics Clinics at the UIHHSS Center for Women’s Health. Potentially eligible women will be identified through clinic schedules and eligibility assessed via Cerner/EHR (only if data is available, data will not be available for new UIC patients). Women identified as potentially eligible through the EHR data or new UIC patients attending their first OB prenatal appointment will be approached in clinic. A research team member will introduce the study, assess interest, and further determine eligibility using a screening checklist. Interested and eligible women will be asked to provide contact information. As part of routine care, maternal hemoglobin will be assessed following the first OB visit. For women that express interest in the study and provide contact information, hemoglobin results will be followed up in Cerner. Women will be called regardless of their results to report on continued study eligibility. If hemoglobin is within the study defined range (10.0 – 11.9 g/dl) women will be invited to participate. Those who continue to express interest will be asked to schedule a baseline appointment at the UIC Clinical Research Center (CRC)s. Women will be consented at the baseline visit. Research personnel will explain to every eligible woman that their choice to participate will in no way affect their standard of care at UIHHS.

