### III. Inclusion/exclusion criteria.

- a. Inclusion criteria: obtaining prenatal care at UIC; initial prenatal hemoglobin between 10.0 – 11.9 g/dl; 18 - 45 years of age; spontaneous/natural conception; singleton pregnancy; < 20 weeks gestation; and willing to: a) fast for at least 2 hours prior to research data collection visits (3 occasions), b) agree to randomization; c) ingest Lp299v + standard PNVI or standard PNVI + placebo daily through delivery; c) refrain from **ALL** other supplements including other PNVs unless medically indicated (e.g., folate); d) attend 3 research data collection visits at UIC; e) undergo 3 venipunctures; and f) come to UIC on 4-5 occasions (separate from research visit but will be coordinated around standard clinical care visits) to pick up supplements and have study compliance monitored/checked. Women will also be able to read and write English, and have access to a smart phone. Also, women must agree to refrain from **ALL** other pre and probiotic supplements (unless medically indicated) including Activia yogurt, Kefir, Tropicana Probiotic, and Good Belly products while in the study.
- b. Exclusion criteria: Autoimmune disorder; current or previous premature rupture of membranes or clinical chorioamnionitis; current bacterial or viral infection; oral antibiotic use in the last 3 months; receiving steroid or anti-inflammatory treatment; previous bariatric surgery; malabsorptive condition; current hyperemesis; hematologic disorder (i.e., sickle cell disease or hemochromatosis); current tobacco use or within the past 1 month; current alcohol consumption; current drug use; or type 1 or 2 diabetes given these factors may influence the biological markers.

**IV. Randomization.** Women will be randomized to the Lp229V + standard PNVI or standard PNVI + placebo following the baseline visit.

**V. Treatment groups.** Women will be assigned to one of two treatment groups as described below.

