## **XII. Data management.**

Research staff will enter all data directly into a Research Electronic Data Capture (RedCap) (Vanderbilt University, Nashville, TN) data structure. Standard checks for outliers, duplicates, and other errors associated with data entry will be conducted. Dietary data will be collected using the online Diet History Questionnaire-II (NCI, Bethesda, MD).

**XIII. Statistical analysis.** Statistical analysis will be performed using SAS (v. 9.4., Cary, NC). Variables not normally distributed will be transformed and if normality not achieved, non-parametric tests will be utilized. Data that are left censored due to undetectable levels will be analyzed using imputation or tobit regression to avoid biased estimates. Descriptive statistics including means, medians and standard deviations for continuous variables and frequency for categorical variables will be used to describe the women, serum, and rectal swabs outcomes at baseline. Differences between treatment groups (Lp299v + standard PNVI vs. standard PNVI + placebo) for the baseline variables will be compared by t-test or non-parametric equivalent with Bonferroni correction and categorical data via chi-square or Fisher exact test. The correlation between the continuous variables at each time-point, baseline, 20 – 24, 34 – 36 and delivery overall and within each group will be assessed by Spearman or Pearson correlation coefficients. A two-way analysis of variance, using a general linear model for repeated measures between treatment groups and time-points will be examined. If significant effects are observed over time, single different pregnancy time-points (i.e., 24 - 28, 34 - 36 gestational week) will be tested. All *P* values were based on a two-sided test of statistical significance accepted at the level of  $P < 0.05$ .

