The rectal swabs microbial 16s rRNA sequencing data will be analyzed with QIIME and PICRUSt. Baseline microbial abundance, diversity, and predicted microbial metabolisms will be assessed. For feasibility, # of charts screened, prescreening eligible, approached, and enrolled will be calculated. The # of visits completed at each time point and end of study attrition will be determined and differences between groups calculated. Adherence (# of pills consumed) and # of SAEs/AEs will be calculated and compared between groups. Maternal stress response, maternal iron-related parameters, and inflammation at baseline, 24-28 weeks, 34-36 weeks and labor and delivery, will be evaluated using repeated measures ANOVA and ANCOVA to adjust for baseline differences. Infant iron status at delivery will be compared between groups (Student's t-test). Microbial abundance, diversity and microbial metabolisms will be compared between groups at baseline, 24-28 weeks, 34-36 weeks (Student's t-test/Mann Whitney U) and within group changes at 24-28 weeks and 34-36 weeks will be determined. The mediating effects of maternal rectal swabs microbiome, systemic inflammation and iron regulatory responses on the relationship between Lp299v on maternal stress- and iron-related outcomes will be explored using generalized linear models. Multiple comparisons and false discovery rate adjustments will be used accordingly.

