#### **XIV. Data and safety monitoring plan.**

The PI will establish a data safety monitoring plan and follow all procedures for the protection of human subjects as required by UIC. The purpose of this data and safety monitoring plan is: (1) to ensure the safety of study subjects and the validity of data; and (2) to produce high quality research while considering both risks and benefits. The PI and research assistants will meet weekly to monitor the components of the research study.

Assessment of study risk. The probiotic proposed for use in the study is not contraindicated during pregnancy and therefore has not been shown to pose any adverse risk to the pregnant woman or her fetus. All other study procedures, based on UIC guidelines should be determined as minimal risk.

Data monitoring plan. The PI will monitor the following items: data quality, completeness, and timeliness; adequacy of compliance with goals for recruitment and retention, including those related to participation of minorities; adherence to the protocol; and adverse events reported by subjects at study and adherence visits. If an adverse event is reported during the study, subjects will be requested to report the event to their physician and the PI. All adverse events will be documented and reported to the UIC IRB in a timely manner based on the type of adverse event (adverse event vs. serious adverse event). We will also record and track reasons for dropout. All authorized study personnel will be required to notify the PI of any unanticipated problems/adverse events immediately upon discovery. The PIs will immediately notify the UIC IRB. The study will be subject to annual review and recertification by the OPRS.

Experimental Aim 2: The Maternal Stress Reduction Project, "Happy Moms" Focus Groups  
Information collected from the focus groups will help inform the development of a curriculum focusing on lifestyle and dietary approaches to reduce chronic stress from structural violence. The curriculum will be developed into a series of classes that will be offered at the New Moms Austin Chicago location. The classes will be open to focus group participants and women currently participating in Family Support programs offered by New Moms.

The Maternal Stress Reduction Project, "Happy Moms": Recruitment, Eligibility, Informed Consent and Data Collection

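### The tolerability verdict compares raw adverse event counts, ignores the baseline GI checklist, has no rule for repeat reports, and leaves out withdrawal because of adverse events

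*Combined protocol and SAP*

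**What the plan says.** Tolerability is part of Specific Aim 4. Section VI.c (Feasibility and Tolerability) sets two conditions: no serious AE, and a similar rate of non-serious AEs in the two arms. Its stated source is remote contact: "Tolerability [(potential adverse events (AEs) (e.g., GI symptoms)] will be assessed via phone/email/text using the Pillsy app weekly for the first 4 weeks", then every two weeks.

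A separate GI checklist is survey 4 at baseline: "This short survey probes for recent GI problems including abdominal pain, nausea, constipation, and diarrhea". It is repeated at the 24–28 and 34–36 week research visits. For the four pill pick-up visits the plan says "We will administer the GI symptoms checklist at each visit". Section XIV also refers to AEs that women report at study and adherence visits.

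The analysis in section XIII is one clause: the number "of SAEs/AEs will be calculated and compared between groups". The ANCOVA adjustment for baseline in that section covers stress response, iron parameters and inflammation, not AEs or GI symptoms.

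On stopping, VI.c treats overall withdrawal and adherence as feasibility criteria, and XIII compares attrition and adherence by group. Section XIV adds "We will also record and track reasons for dropout". None of this enters the tolerability rule.

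**The concern.** Abdominal pain, nausea, constipation and diarrhea are the checklist items, and women who already have them can enrol; of the exclusions, only current hyperemesis and a malabsorptive condition bear directly on GI complaints. A raw AE count mixes symptoms that preceded the first dose with symptoms that followed it. It also lets one woman with one lasting symptom contribute many events.

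The plan leaves three things open: whether women or events are counted, whether repeat reports of one symptom are merged, and whether checklist answers become AEs. An analyst could settle these after seeing the data.

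An AE that leads a woman to withdraw is arguably the clearest sign of poor tolerability. Here it weighs no more than a mild passing symptom. At stake is whether the Aim 4 conclusion reflects the capsule or the baseline mix of two small groups.

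**Working it through.** The plan gives no margin, power or expected AE rate for tolerability, so there is no figure to reproduce. Rates below are assumptions.

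**Inputs from the plan.** Section 2.I: "We will recruit and enroll 40 women early in pregnancy". Section IV: "Women will be randomized to the Lp229V + standard PNVI or standard PNVI + placebo following the baseline visit". The ratio is not stated; 1:1 is assumed, giving n = 20 per arm. Dosing starts at 15–20 weeks and runs to delivery. Pick-ups are at about 18–19, 22–23, 30–31 and 38–39 weeks.

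**1. Chance imbalance at baseline.** Let X and Y be the numbers of women with a GI symptom at baseline in each arm, independent Binomial(20, p). The SD of X − Y is √(2 × 20 × p(1 − p)), and P(|X − Y| ≥ 3) is summed exactly.

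| Assumed p | SD (women) | P(imbalance ≥ 3) |
|---|---|---|
| 17.5% | 2.40 | 0.29 |
| 30% | 2.90 | 0.39 |
| 50% | 3.16 | 0.43 |

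**2. Recording occasions per woman.** Assume delivery at 39–40 weeks and attendance at every contact.
- Start at week 15: 24–25 weeks of dosing. Remote contacts: 4 + (20 or 21)/2, rounded down = 14. Checklists: 4 pick-ups + 2 research visits = 6. Total 20.
- Start at week 20: 19–20 weeks of dosing. Remote contacts: 4 + (15 or 16)/2, rounded down = 11–12. The 18–19 week pick-up comes before the first dose, so checklists = 5. Total 16–17.

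The range of 16–20 is a ceiling. It needs checklist answers to count as AEs and a report on every occasion. Remote contacts alone give 11–14.

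**3. Effect of repeat counting.** Suppose raw counts A and B are compared as independent events, z = |A − B|/√(A + B). If each symptomatic woman reports K times, z is √K times its value with each woman counted once. Example: 8 versus 5 symptomatic women and no treatment effect. Counted once, z = 3/√13 = 0.83. With K = 16 the counts are 128 and 80, and z = 48/√208 = 3.33.

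With no treatment effect, 30–50% of women having a persistent symptom, K = 16–20 and reporting on half to all occasions, a nominal two-sided 5% comparison gives a false positive about 36–61% of the time. The plan does not name this test; the figure shows what an unmerged count permits.

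**4. What the baseline reference gains.** Assume 60% of women have a symptom at baseline, and new-onset risk among the other 40% is 30% versus 10%.
- Any symptom: 0.60 + 0.40 × 0.30 = 72% versus 0.60 + 0.40 × 0.10 = 64%. Difference 8 points; SE = √[(0.72 × 0.28 + 0.64 × 0.36)/20] = 0.147.
- New symptoms only: 12% versus 4%. Difference 8 points; SE = √[(0.12 × 0.88 + 0.04 × 0.96)/20] = 0.085.

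The difference is the same and the SE is 42% smaller. With 80% at baseline both differences are 4 points and the SE falls from 0.116 to 0.062, or 47%. On these inputs the gain is precision.

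**The case against.** The strongest reply is that this is a placebo-controlled pilot randomized after baseline, so existing symptoms cannot bias the comparison systematically. The verdict is also descriptive: similar has no margin or test, so no imbalance mechanically decides it. Both points stand. They limit the concern to noise and analyst choice, but at 20 per arm the noise is not small.

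Three stronger readings are tempting, and the documents do not support them.
- A reader might infer that a woman constipated at baseline adds an AE at every contact and visit. VI.c names only the remote contacts, the checklist is listed as a survey, and no text turns its answers into AEs. Pooling is an unresolved ambiguity, not a stated rule.
- A reader might infer that counting baseline symptoms hides most of a real difference and that the fix restores it. Step 4 shows the same difference before and after when new-onset risk applies only to women without symptoms at baseline. A larger recovery needs assumptions about new events in women already symptomatic, and the documents give no such rates.
- A reader might infer that intolerance leading to stopping goes unseen. Symptoms are asked about at remote contacts, attrition and adherence are compared by arm, and dropout reasons are kept. The gap is that these play no part in the tolerability rule.

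It is also fair to object that the checklist is not described as grading severity, so worsening may not be derivable, and that no item set is given for the remote contacts, which may limit merging by symptom.

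**Conclusion.** The point holds as a weakness in how tolerability is counted and should be corrected; it is not a source of systematic bias. The verdict rests on a raw AE comparison that uses no baseline reference, sets no rule for repeats and gives no weight to AE-related withdrawal. The size is a 0.29–0.43 chance of a baseline imbalance of three or more women (20 per arm, assumed prevalence 17.5–50%) and a ceiling of about 16–20 records of one persistent symptom per woman. Unmerged counts treated as independent would give false positives of roughly 36–61% under the assumptions in step 3. Prevalence, reporting frequency, 1:1 allocation and delivery at 39–40 weeks are assumptions. Similar remains undefined, and a better count does not settle that.

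**What to change.** In VI.c and XIII:
- For GI symptoms, compare by arm the number of women with at least one checklist symptom that was absent at baseline and appears after the first dose. Count each woman once per symptom across remote contacts, pick-ups and research visits. Count worsening of a baseline symptom only if the checklist records severity.
- Report other non-serious AEs as the number of women with at least one event.
- Add to the tolerability criterion the number of women per arm who withdraw because of an AE, taken from the dropout reasons already recorded under XIV.

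The cost is protocol wording and a small programming step on data largely collected already, with no extra visits. Fewer events will be counted, and the verdict may be less favourable if AE-related withdrawal differs by arm. Counting women who stop the capsule but stay in the study would need one added field, because the plan records reasons only for dropout.
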